726 A blood sample will be drawn to send to the central laboratory for a random, non-fasting C-peptide
727 determination to characterize baseline residual insulin production. In conjunction, blood glucose
728 may be measured using a blood glucose meter or a blood sample may be drawn to send to the
729 central laboratory for a blood glucose assessment.

730 **4.1.3 Randomization**

731 Eligible participants will be randomly assigned to one of two treatment groups in a 3:1 ratio:

- 732 1. Control-IQ Closed-Loop Control (CLC) Group
- 733 2. Standard of Care (SC) Group

734 The participant's randomization group assignment is determined by completing a Randomization
735 Visit case report form on the study website. The randomization list will use a permuted block
736 design, stratified by clinical center.

737 *The participant will be included in the data analysis regardless of whether or not the protocol for
738 the assigned randomization group is followed. Thus, the investigator must not randomize a
739 participant until he/she is convinced that the participant/parent will accept assignment to either
740 of the two groups.*

741 *It was decided that it was more important to stratify randomization by clinical center than by
742 factors such as baseline time in range, HbA1c, or device use since these factors will be easier to
743 adjust for in analysis than will clinical center in view of the relatively small number at each clinical
744 center.*

745 **4.1.4 Questionnaires**

746 Participants will complete a set of baseline questionnaires, described in section 8.2 adapted for
747 age, prior to randomization.

748

Chapter 5: Main Study Procedures

749 **5.1 Procedures for the CLC Group**

750 Participants assigned to the CLC group will receive study system training. These training
751 sessions can occur on the same day or extend to up to one additional day if needed within 1-7
752 days from randomization; participants will not take the study system home until training has
753 been completed.

754 The parent/guardian will be trained on severe hypoglycemia emergency procedures including
755 removal of the study pump and administration of glucagon. The parent/guardian will be asked to
756 attend any/all of the other training procedures.

757 **5.2 Study System Training**

758 Participants will receive study system training by a qualified trainer. The study system includes
759 the Tandem t:slim X2 with Control-IQ technology and associated Dexcom G6 CGM.

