Comment	Screen/ Enroll	Run-in	Rand									
Eligibility Assessment	X	X	X									
HbA1c (DCA Vantage or similar point of care device, or local lab)	X		X									X ¹⁷ 18
HbA1c (Central lab)			X									X
C-peptide (Central lab) and blood glucose assessment			X									
Pregnancy test (females of child-bearing potential)	X		X					X				X ¹
Device Data download(s)	X	X	X	X	X	X	X	X	X	X	X	X
Review diabetes management and AEs		X	X	X	X	X	X	X	X			X ²⁵ 24
Questionnaires			X									X

26 **2. Statistical Hypotheses**

27 The primary outcome for this study is CGM-measured % in range 70-180 mg/dL over a 16-week period.
28 The intervention will be considered effective if the Closed-Loop Control [CLC] is superior to the
29 Standard Care [SC] using a statistical significance of $\alpha=0.05$ and the model specified below in Section 6
30 (i.e., $p < 0.05$).

31 The null/alternative hypotheses are:

32 1. *Null Hypothesis*: There is no difference in mean CGM-measured % in range 70-180 mg/dL over
33 16 weeks between SC and CLC
34 2. *Alternative Hypothesis*: The mean CGM-measured % in range 70-180 mg/dL over 16 weeks is
35 different for SC and CLC.

36 **3. Sample Size**

37 Sample size has been computed for the primary outcome (CGM-measured % in range 70-180 mg/dL).
38 Data from IDE G170267; Device Name: t:slim X2 with Control-IQ Technology; “Real-Time Monitoring
39 and Glucose Control During Winter-Sport Exercise in Youth with Type 1 Diabetes: The AP Ski Camp
40 Continued” were used to calculate sample size specific to this age group. In this study, which was
41 completed in the winter of 2018, 24 school-aged children (6-12 years) with type 1 diabetes participated in
42 a 3-day ski camp (~5 h skiing/day), followed by an additional 72 hour at-home phase under parental
43 supervision. Study participants were randomized 1:1 to SAP and t:slim X2 with Control-IQ Technology.
44 The data from the 72-hour home phase was used for this sample size calculation – *note that the closed-
45 loop control system and the age range of the participants are identical to those proposed in this
46 application*:

Results from home phase of G170267	Control IQ	SAP	F	p value
Percent between 70 and 180mg/dl	71 ± 6.6	52.8 ± 13.5	16.4	0.001

47

48 From the DCLP1 study using the same algorithm in an older cohort, the effective standard deviation (after
49 adjusting for the correlation between baseline and follow up) for time in range 70-180 mg/dL over the

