50 course of 6 months was 6% (95% CI 5% to 7%) for the CLC group and 7% (95% CI 6% to 8%) for the
51 SAP group.

52 A total sample size was computed to be N=60 for the following assumptions: (1) 3:1 [CLC:SC]
53 randomization, (2) 90% power, (3) a 10% absolute increase in % time in range 70-180 mg/dL, (4) an
54 effective SD of 10%, and (5) 2-sided type 1 error of 0.05.

55 The total sample size has been increased to N=100 to account for dropouts and to increase the number of
56 participants who will be exposed to the CLC system for an enhanced safety and feasibility assessment.

57 **4. Efficacy Outcome Measures**

58 **4.1. Primary Endpoint:**

59 • CGM-measured % in range 70-180 mg/dL

60 **4.2. Secondary Endpoints**

61

63 **4.2.1. Hierarchical Endpoints**

64 The following secondary endpoints will be tested in a hierarchical fashion between the two intervention
65 arms as described in Appendix.

66

- CGM-measured % above 180 mg/dL
- CGM-measured mean glucose
- HbA1c at 16 weeks
- CGM-measured % below 70 mg/dL
- CGM-measured % below 54 mg/dL
- CGM-measured % above 250 mg/dL
- Glucose variability measured with the coefficient of variation (CV)

74 **4.2.2. Other Secondary Endpoints**

75 The following endpoints are considered exploratory.

77

- CGM-Measured
 - % in range 70-140 mg/dL
 - glucose variability measured with the standard deviation (SD)
 - % <60 mg/dL
 - low blood glucose index (LBGI)*
 - hypoglycemia events (defined as at least 15 consecutive minutes <70 mg/dL)
 - % >300 mg/dL
 - high blood glucose index (HBGI)*
 - % in range 70-180 mg/dL improvement from baseline to 16 weeks ≥5%
 - % in range 70-180 mg/dL improvement from baseline to 16 weeks ≥10%
- HbA1c
 - HbA1c <7.0% at 16 weeks
 - HbA1c <7.5% at 16 weeks
 - HbA1c improvement from baseline to 16 weeks >0.5%
 - HbA1c improvement from baseline to 16 weeks >1.0%
 - HbA1c relative improvement from baseline to 16 weeks >10%
 - HbA1c absolute improvement from baseline to 16 weeks >1.0% or HbA1c <7.0% at 16 weeks
- Insulin
 - Total daily insulin (units/kg)
 - Basal: bolus insulin ratio
- Weight and body mass index (BMI)
- Questionnaires
 - Fear of Hypoglycemia Survey (HFS-II) – total score, 2 subscales and 4 factor scores:
 - Behavior
 - Avoidance
 - Maintain high BG
 - Worry
 - Helplessness
 - Social consequences
 - Clarke Hypoglycemia Awareness Scores

- 108 ○ Problem Areas In Diabetes Survey (PAID)
- 109 ○ INSPIRE survey scores
- 110 ○ PedsQL Diabetes Module – total score and 5 subscales:

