220 that all statistical methods for handling missing data rely on untestable assumptions and there is no one
221 correct way to handle missing data. Our goal is to minimize the amount of missing data so that the
222 results will not be sensitive to which statistical method is used.

223 To that end, sensitivity analyses will be performed to explore whether results are similar for primary
224 analysis when using different methods. The following methods will be applied:

- 225 • Rubin's multiple imputation with treatment group in the imputation model
- 226 • Available cases only
- 227 • Multiple imputation with pattern mixture model assuming the dropout trajectory of the CLC
228 group was that of the SC group (Mallinckrodt and Clark, 2003)

229 **6. Efficacy Analysis**

230 **6.1 Primary Analysis**

231 This study primary outcome is CGM measured % time in range 70-180 mg/dL over 16 weeks.

232
233 Summary statistics (mean \pm SD or median (quartiles)) will be reported by treatment group for the CGM-
234 measured % in range 70-180 mg/dL at baseline, 16 weeks intervention and change from baseline to 16-
235 week intervention.

236 Changes from run-in pre-randomization CGM wear to the 16-week post-randomization period in CGM-
237 measured % in range 70-180 mg/dL between two treatment arms will be compared using a linear mixed
238 effects regression model while adjusting for baseline CGM-measured % in range 70-180 mg/dL, age,
239 prior CGM and pump use, and clinical center (random effect). A point estimate, 95% confidence interval
240 and two-sided p-value will be reported for the treatment effect based on the linear regression model and
241 a 5% level will be used to declare statistical significance. Residual values will be examined for an
242 approximate normal distribution. If values are highly skewed then a transformation or robust statistical
243 methods will be used instead. However, previous experience suggests that the residual values for % time
244 glucose in target range will follow an approximately normal distribution.

245 Imbalances between groups in important covariates are not expected to be of sufficient magnitude to
246 produce confounding. However, the presence of confounding will be evaluated in the sensitivity
247 analyses by including factors potentially associated with the outcome for which there is an imbalance
248 between groups (Section 5).

249 Missing Data

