250 In the primary analysis, any missing data at baseline or follow-up will be handled using direct
251 likelihood. A longitudinal linear regression model will be fit with the percent of time in range at
252 baseline and follow-up as the dependent variable. This model will adjust for age, prior CGM use and
253 pump use as fixed effects and clinical center as a random effect. This model adjusts for baseline time in
254 range by forcing the treatment groups to have the same mean value at baseline.

255

256 **6.2 Analysis of the Secondary Endpoints**

257 **6.2.1 Hierarchical Analyses**

258 To preserve the overall type 1 error for selected key secondary endpoints, a hierarchical testing
259 procedure will be used. If the primary analysis for time in range described above results in a statistically
260 significant result ($p < 0.05$), then testing (similar to the model described above for the primary outcome)
261 will proceed to the next outcome metric in the following order:

- 262 • CGM-measured % in range 70-180 mg/dL (primary outcome)
- 263 • CGM-measured % above 180 mg/dL
- 264 • CGM-measured mean glucose
- 265 • HbA1c at 16 weeks
- 266 • CGM-measured % below 70 mg/dL
- 267 • CGM-measured % below 54 mg/dL
- 268 • CGM-measured % above 250 mg/dL
- 269 • Glucose variability measured with the coefficient of variation (CV)

270

271 This process continues iteratively moving to the next variable down on the list until a non-significant
272 result ($p \geq 0.05$) is observed, or all eight variables have been tested. If a non-significant result is
273 encountered, then formal statistical hypothesis testing is terminated and any variables below on the list
274 are not formally tested (see example in the Appendix).

275 Regardless of the results of the hierarchical testing, summary statistics appropriate to the distribution
276 will be tabulated by treatment arm for each hierarchical outcome. A 95% confidence interval for the
277 treatment arm difference will also be calculated for all seven hierarchical secondary outcomes listed
278 above. However, a confidence interval that excludes zero will not be considered a statistically
279 significant result if an outcome variable higher on the hierarchical list failed to reach statistical
280 significance.

281 Analysis for each of the CGM metrics listed above for the hierarchical analysis will parallel the analysis
282 described for the primary outcome in Section 6.1.

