283 For the HbA1c analysis, change in HbA1c from baseline to 16 weeks will be compared between the two
284 treatment arms using a linear model while adjusting for baseline HbA1c, age, prior CGM and pump use,
285 and clinical center (random factor). Missing data will be handled using direct likelihood in a regression
286 model including all available central laboratory HbA1c measurements at baseline and 16-week visits.
287 When available, the local HbA1c measurement will be included in the regression model as an auxiliary
288 variable.

289 For all above analyses, regression diagnostics will be employed analogous to as described in Section 6.1
290 for the primary outcome.

291 **6.2.2 Other Secondary Analyses**

292 For all other secondary endpoints, only participants with non-missing data will be included in analyses
293 (available cases method). Summary statistics (mean \pm SD, median (IQR) or n (%)) appropriate to the
294 distribution will be tabulated for them at baseline, 16 weeks and for the changes from baseline to 16
295 weeks. For continuous outcomes, linear regression models will be used to compare the treatment effects
296 while adjusting for corresponding baseline values (e.g., baseline % in range 70-140 mg/dL for
297 comparing change in % in range 70-140 mg/dL from pre-randomization CGM wear to 16 weeks post-
298 randomization period), age, prior CGM and pump use, and clinical center as a random effect.
299 Comparisons of body weight and BMI will also be adjusted for gender.

300 *Binary CGM and HbA1c Outcomes*

301 For the binary HbA1c outcomes listed in Section 4, risk-adjusted percentages by treatment group will be
302 computed at 16 weeks from a logistic regression model. The logistic regression will adjust for baseline
303 HbA1c (as a continuous factor), age, prior CGM and pump use as fixed effects, and clinical site as a
304 random effect. Similar analyses will be done for the binary CGM outcomes in Section 4.

305 *Questionnaires*

306 For each questionnaire, mean \pm SD or percentiles appropriate to the distribution will be given by
307 treatment group at baseline and 16 weeks. Group comparisons will be conducted for the total score
308 (mean score) and subscales from participant version and parent version separately using similar linear
309 models as described above. The SUS survey and the INSPIRE post-treatment survey will only be
310 administered to the CLC group at the 16-week visit, and thus the scores will only be tabulated.

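### Baseline HbA1c, named in the protocol as easy to adjust for, is absent from the primary and hierarchical CGM models; adding it is a nearly free gain in precision, not the repair of an error

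*SAP*

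**What the plan says.** Protocol 4.1.3 uses permuted blocks stratified by clinical center. It explains that center was preferred to "factors such as baseline time in range, HbA1c, or device use since these factors will be easier to" adjust for than center, given the small numbers at each site.

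The primary model in SAP 6.1 is a linear mixed "effects regression model while adjusting for baseline CGM-measured % in range 70-180 mg/dL, age", prior CGM and pump use, and center as a random effect. Protocol 11.6 lists the same covariates. The missing-data paragraph of SAP 6.1 recasts this as a longitudinal model with baseline and follow-up time in range both as outcomes and a common baseline mean: "This model will adjust for age, prior CGM use and" pump use, with center random. HbA1c appears in neither description.

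The six hierarchical CGM endpoints follow the same pattern, each with its own baseline metric (Protocol 11.7, SAP 6.2.1). The HbA1c endpoint compares the "treatment arms using a linear model while adjusting for baseline HbA1c, age, prior CGM and pump use" and center, without baseline time in range.

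A fallback exists. Protocol 11.5.2 and SAP 5.2 add baseline characteristics judged imbalanced, on clinical judgement and not a p-value, as a sensitivity analysis of the primary endpoint. SAP 5.2 takes the candidate factors from Section 11. In the SAP, Section 11 is Device Issue; the baseline list, which includes HbA1c, is Section 10.

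**The concern.** The reason given for not stratifying on the three named factors has force to the extent that they are then adjusted for. In the primary model two of the three are, and HbA1c is not. Yet Protocol 4.1.1 has central-lab HbA1c drawn at randomization for use in outcome analyses, Protocol 2.1 sets recruitment minimums on either side of about 8%, and SAP 13 uses baseline HbA1c as a subgroup factor for time in range.

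HbA1c might add to the CGM baseline. That baseline covers only two weeks (SAP 4.3), is set to missing below 168 hours of data, and for pump-naive children can fall soon after pump start and dose changes (Protocol 3.3). Whether it does add anything is not shown in the documents.

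At stake is some precision in the primary estimate and in the hierarchy, where the HbA1c test stands ahead of four later tests and no power is given for any secondary. A second, smaller matter is that an HbA1c-adjusted estimate would appear only if someone judged the arms imbalanced, so it would arise from a look at the data and not from the plan.

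**Working it through.** **Inputs.** From SAP section 3: "A total sample size was computed to be N=60 for the following assumptions: (1) 3:1 [CLC:SC"] "randomization, (2) 90% power, (3) a 10% absolute increase in % time in range 70-180 mg/dL, (4) an" "effective SD of 10%, and (5) 2-sided type 1 error of 0.05". The planned total is 100, so 75 CLC and 25 SC. The effective SD in the older cohort is described as the value after "adjusting for the correlation between baseline and follow up) for time in range 70-180 mg/dL over the" follow-up period. I read the planning SD of 10 in the same sense, already net of baseline time in range. The partial R2 of baseline HbA1c given the current covariates is not in the documents. I assume 0.02 to 0.10 as the main range and show 0 to 0.30.

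**The plan's own figure.** SC group = (1 + 1/3) × (1.960 + 1.282)² × (10/10)² = 14.01, rounded up to 15. With 45 CLC the total is 60, which reproduces the plan. The t-based power is 91.0% at 60 and 88.9% at 56.

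**Planned model at N=100.** SE = 10 × sqrt(1/75 + 1/25) = 2.31. The 95% CI half-width is 1.96 × 2.31 = 4.53 points. Power for a 10-point difference is 99.1% (normal approximation) or 99.0% (t-based).

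**With HbA1c added.** Residual SD = 10 × sqrt(1 − R2), and SE and half-width shrink in proportion. The last column is the SD of that part of the current estimate's error that comes from chance HbA1c imbalance not explained by the present covariates: sqrt(R2) × 2.31.

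| Partial R2 (assumed) | SD | SE | CI half-width | Narrowing | Power | SD of chance component |
|---|---|---|---|---|---|---|
| 0 | 10.00 | 2.31 | 4.53 | none | 99.1% | 0 |
| 0.02 | 9.90 | 2.29 | 4.48 | 1.0% | 99.2% | 0.33 |
| 0.05 | 9.75 | 2.25 | 4.41 | 2.5% | 99.4% | 0.52 |
| 0.10 | 9.49 | 2.19 | 4.29 | 5.1% | 99.5% | 0.73 |
| 0.16 | 9.17 | 2.12 | 4.15 | 8.3% | 99.7% | 0.92 |
| 0.30 | 8.37 | 1.93 | 3.79 | 16.3% | 99.9% | 1.26 |

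In sample-size terms, R2 of 0.02 to 0.10 is worth 1/(1 − R2) − 1 = 2% to 11% more participants. For that range, 95% of the chance component lies within 1.96 × 0.33 = 0.64 to 1.96 × 0.73 = 1.43 points, against a planned effect of 10.

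**Validity of the planned model.** The chance component is already inside the SE of 2.31. For R2 = 0.10, 0.73² + 2.19² = 5.33 = 2.31². A simulation under the null (10,000 trials per scenario, 75:25, R2 of 0.05 and 0.10, HbA1c correlated −0.5 or −0.7 with baseline time in range) gave a mean error within 0.04 points and type I error of 5.1% to 5.3% for the model without HbA1c.

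**The case against.** The strongest case against is that nothing here is inconsistent. A reader might infer from Protocol 4.1.3 that adjustment for HbA1c was promised and then dropped. The text does not say so: it compares ease of adjustment in order to justify stratifying by center, names the factors only as examples, and commits none of them to the primary model. Protocol 11.6 and SAP 6.1 agree with each other. This stands.

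A reader might also infer that a chance HbA1c imbalance would bias the result. It would not. Under randomization it is ordinary sampling variation, covered by the planned CI.

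Nor is the effect of an imbalance as large as a quick calculation suggests. Taking a 2-SE imbalance (2 × 0.231 = 0.46 SD) and assumed partial correlations of 0.2 to 0.4 gives 0.46 × 10 × 0.2 to 0.4 = 0.9 to 1.8 points. That applies a partial correlation to a raw imbalance, part of which baseline time in range absorbs. If the two correlate at 0.5 to 0.8 (assumed), the expected shift is multiplied by sqrt(1 − 0.5²) = 0.87 down to sqrt(1 − 0.8²) = 0.60, giving about 0.55 to 1.6 points. An imbalance that size is also roughly a 1-in-20 event.

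The gain itself is assumed. The older cohort's SDs of 6 and 7 would make it smaller still in points, and the documents offer no figures for the secondaries. That stands too.

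Finally, an ordinary covariate would drop children without a baseline HbA1c, against the SAP 5.1 rule that all randomized participants are included. This is a fair practical point, and a stated missing-value rule answers it.

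The argument that the fallback suffices is weaker. The fallback is conditional, never becomes the primary result, does not reach the hierarchical endpoints, and read literally draws its factors from a section without baseline variables.

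**Conclusion.** The concern holds as an optional improvement in precision. For an assumed partial R2 of 0.02 to 0.10 the primary CI narrows by about 1% to 5%, and by about 8% at 0.16. If HbA1c adds nothing beyond baseline time in range, there is no gain. Power rises by less than one percentage point in every case because it is already about 99%. These figures rest on the planning SD of 10, on 75:25 with no dropout, and on an R2 range that the documents do not supply. For the hierarchical endpoints the direction is the same, but its size cannot be given.

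The documents do not support calling the primary analysis biased, underpowered or in breach of the protocol. The one outright slip is the SAP 5.2 cross-reference to Section 11.

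**What to change.** - In SAP 6.1 and 6.2.1, and in Protocol 11.6 and 11.7 to match, add baseline central-lab HbA1c as a prespecified continuous covariate in the primary and six hierarchical CGM models. In the longitudinal form give it its own coefficient at follow-up, so that its relation to the 16-week value is not forced to equal its relation to the baseline value.
- Add baseline % 70-180 mg/dL to the HbA1c model.
- State that a missing baseline covariate value is filled without using treatment arm (for HbA1c, from the local measurement or else by imputation) or is modelled jointly, so that every randomized participant stays in the analysis.
- Correct the SAP 5.2 cross-reference from Section 11 to Section 10.

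The cost is about one degree of freedom, one missing-covariate rule and matching wording in both documents. No new data are needed. The changes should be fixed before outcome data are seen by arm.
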